## 6.3 Phase II component of the trial

Based on the phase Ib and data from other studies of taselisib, the recommended dose of taselisib for phase II is 4 mg. Note that dose reduction within patients (individually) is allowed. Dose reduction will be required for a given patient in case of grade 3 or 4 toxicities.

The primary efficacy endpoint is clinical benefit rate (CBR) of enzalutamide + taselisib in patients with androgen receptor positive triple negative metastatic breast cancer. Secondary objectives are to determine the ORR and progression free survival (PFS). CBR is defined as the proportion of patients achieving a complete response (CR) plus partial response (PR) plus stable disease (SD)

for at least 16 weeks. To assess objective responses, we will estimate the overall tumor burden at baseline to which subsequent measurements [performed every 2 cycles using the Solid Tumor Response Criteria (RECIST) v1.1] will be compared.

Section 6.3.1 and 6.3.2 discuss administration of taselisib and enzalutamide. Patients on the combination arm can take both drugs at the same time. Patients on the enzalutamide only arm should take enzalutamide only as directed below.

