## 7.2 Taselisib

See Table 3 at the end of this section for taselisib dose modification criteria

Patients who experience an SAE or whose treatment is interrupted or permanently discontinued due to an adverse event or clinically significant laboratory value must be followed as outlined in Table 3 below, at least once a week for 4 weeks, and subsequently at 4-week intervals, until resolution or stabilization of the event, whichever comes first. If a patient requires a dose delay of > 28 days from the intended day of the next scheduled dose, then the patient should be discontinued from the study. All patients must be followed for adverse events and serious adverse events for 30 days following the last dose of taselisib. This can be done as either an in-office visit or by phone. If the taselisib dose is reduced due to an adverse event which is later determined to be secondary to enzalutamide and enzalutamide is discontinued, taselisib can be re-escalated at the discretion of the treating physician after consultation with the Protocol Chair. If both taselisib and enzalutamide are held for an adverse event, enzalutamide should be restarted at the original dose. Taselisib should be restarted at one dose lower than the last dose. After 28 days, if the patient is tolerating both medications well, taselisib may be increased back to the original dose.

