#### 7.2.1.5 Liver Toxicity

If clinical symptoms or signs suggestive of liver dysfunction occur (e.g., nausea, vomiting, abdominal pain, fatigue, anorexia, “flu-like” symptoms, dark urine, jaundice, or right upper quadrant tenderness), the serum transaminases should be measured immediately. Elevations above baseline should prompt an evaluation should occur to determine the cause of the elevation, including progressive disease and hepatotoxicity from concurrent medications.

If transaminases (ALT/AST) are elevated  $> 3X$  ULN and are thought to be secondary to disease progression, a CT scan should be obtained to confirm disease progression and the patient should be removed from study. If transaminases (ALT/AST) are elevated  $> 3X$  ULN and not thought to be secondary to disease progression, treatment should be withheld until levels fall to  $\leq 3X$  normal levels. If a patient has known liver metastases and baseline transaminases were 3-5X ULN, treatment should be held until levels fall to less than or equal to baseline levels. If total bilirubin is elevated  $> 1.5$  x normal level, treatment should be withheld until level falls to  $\leq 1.5$  x normal levels. If alkaline phosphatase is elevated  $> 2.5$  x normal value, treatment should be withheld until levels fall to  $\leq 2.5$  x normal level (unless bone metastases are present in the absence of liver metastases). A dose reduction should then be administered following resolution of any or all of these liver enzyme abnormalities.

If transaminases are subsequently elevated  $> 3X$  ULN or, if total bilirubin is elevated  $> 1.5X$  normal value, or if alkaline phosphatase is elevated  $> 2.5$  x normal value (unless bone metastases are present in the absence of liver metastases), treatment will again be withheld until AST/ALT decrease to  $\leq 3X$  normal, total bilirubin decreases to  $\leq 1.5$  x normal value and alkaline phosphatase decreases to  $\leq 2.5$  x normal value. A second dose reduction should then be administered. If a patient has known liver metastases and baseline transaminases were 3-5X ULN, treatment should be held until levels fall to less than or equal to baseline levels. For any hepatic toxicity CTCAE Grade 4, or CTCAE Grade 3 that does not resolve within 7 days to CTCAE Grade  $\leq 1$  (or CTCAE Grade  $\leq 2$  if liver infiltration with tumor present), an abdominal CT scan should be performed to assess if it is related to disease progression.

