Grade 3	
First Occurrence:
 
 
• Hold taselisib and initially manage with antidiarrheals.
 
• Obtain stool culture for infectious workup.
 
• For Grade 3 diarrhea or colitis, treat with systemic corticosteroids (prednisone 60-80 mg QD equivalent or solumedrol 16-20 mg IV q 8 h to start). Can increase steroid dosage if diarrhea does not improve.
 
• Concurrent infections (e.g., Clostridium difficile, enteric bacteria, CMV) should be treated with the appropriate antibiotic.
 
• For patients that do not improve upon 48 hours of corticosteroid treatment, a colonoscopy is recommended to evaluate for other causes of diarrhea (e.g. CMV colitis)
 
 
If diarrhea or colitis improves to Grade <math>\leq</math>1 and upon completion of any steroid taper or antibiotic treatment, resume taselisib treatment at one dose level lower.
 
Second Occurrence:
 
 
• Discontinue taselisib
 

Grade 4	
 
• Discontinue taselisib.
 

Rash	

Special considerations	
 
Permanently discontinue for any rash with concurrent signs/symptoms strongly suggestive of a severe Type 1 hypersensitivity or anaphylactic/anaphylactoid reaction, fever, or with painful desquamation or mucosal involvement suggestive of Stevens-Johnson Syndrome/ toxic epidermal necrolysis, or with other life-threatening complications
 

Grade 1	
 
Continue dosing at current dose and monitor for change in severity (consider contacting patient between study visits). Consider prescribing topical steroidsc.
 

Grade 2	
 
Monitor closely for change in severity and hypersensitivity-related systemic symptoms (contact patient weekly between study visits)
 
Consider prescribing topical steroidsc
 
Consider dermatological consultation
 
Consider one or more of the following:               
 
Hold dose until resolution to <math>\leq</math> Grade 1, then resume at next lower dose level
 
Dose reduction
 
Initiation of oral steroid treatment unless contraindicatedd, monitor blood sugar carefully if initiating steroids while continuing taselisib
 
 
 

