Grade 3: first event	
 
Hold dose and monitor closely for changes in severity and for hypersensitivity-related systemic symptoms
 
Recommend topical steroidsc
 
Recommend initiating oral steroids unless contraindicatedd
 
Upon resolution to <math>\leq</math> Grade 1, reduce to next lower dose level
 
Consider dermatological consultation
 
Consider obtaining photographs of rash if permitted by local regulations
 

Grade 3: first recurrence after dose reduction	
 
Hold dose and monitor closely for changes in severity and for hypersensitivity-related systemic symptoms
 
Recommend initiating oral steroids unless contraindicatedd
 
Discuss with Protocol Chair if would like to consider restarting at next lower level upon resolution to <math>\leq</math> Grade 1, or permanently discontinue
 
Recommend dermatological consultation, if not already performed
 
Consider obtaining photographs of rash if permitted by local regulations
 

Recurrent Grade 3 or Grade 4	
 
Manage as described above.
 
Discontinue taselisib permanently.
 

Hyperglycemia	
For all grades	
 
Instruct patient to follow dietary guidelines provided by the American Diabetes Association
 
For <math>\geq</math> grade 2, initiate, continue or intensify medication with appropriate anti-diabetic treatment (Note: some oral anti-diabetic drugs are CYP3A inducers or inhibitors and should be used with caution)
 
Metformin is the first antihyperglycemic medication of choice because of the lower risk of hypoglycemia with this agent. Because metformin in some patients may also cause diarrhea and not be well tolerated, other antihyperglycemic medications such as sulfonylureas (e.g., glimepiride, glipizide) can be used. Extra caution should be used with other drugs such as sulfonylureas because of the increased risk for hypoglycemia with these agents. Consultation with an endocrinologist can be helpful in managing hyperglycemia.
 
If Grade worsens start following recommendations for the worsened grade
 

Grade 1	
 
Maintain dose level, check FPG every week for 2 weeks, then continue checking every 2 weeks until resolved
 

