### 7.3.2 Other toxicities

Asthenia/fatigue, back pain, diarrhea, arthralgia, hot flush, peripheral edema, musculoskeletal pain, headache, upper respiratory infection, muscular weakness, dizziness, insomnia, lower respiratory infection, spinal cord compression and cauda equina syndrome, hematuria, paresthesia, anxiety, and hypertension have all occurred on studies of enzalutamide.

Though not expected, if  $\geq$  grade 3 diarrhea occurs that is not controlled with anti-diarrheal agents (e.g. loperamide), enzalutamide should be withheld until resolution to  $\leq$  grade 1, then reinstated at the next lower dose level.

If toxicities are  $\leq$  grade 2, manage symptomatically if possible and retreat without dose reduction.

If toxicities are  $\geq$  grade 3, except for anemia, treatment should be withheld until resolution to  $\leq$  grade 1 or baseline if baseline was greater than grade 1, then reinstated, if medically appropriate, at the next lower dose level.

For any grade 3 or 4 toxicity not mentioned above, treatment should be withheld until the patient recovers completely or to grade 1 toxicity. The treatment should then be resumed at the next dose level. For grade 1 or 2 toxicities, no dose reduction should be made.

A maximum of two weeks will be permitted for resolution of grade 3 or 4 toxicities. If toxicity has not resolved by the end of two weeks, patient will be taken off study.

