## 7.4 Special Considerations

- For toxicities which are considered by the treating investigator unlikely to develop into serious or life-threatening events (e.g. alopecia, altered taste etc.), treatment may be continued at the same dose without reduction or interruption.
- The treating investigator may reduce a subject's dose for a toxicity of any grade/duration where s/he believes it to be in the best interests of the subject.
- Any consideration to modification of the above dose modification guidelines should be discussed with the Protocol Chair for approval or disapproval in advance.
- Study participants should be given instructions to minimize sun exposure (i.e. use SPF  $\geq$  30 sunblock, wear hats and long-sleeve clothing) due to the possibility of photosensitivity.
- As referenced above, pneumonitis has rarely been reported in clinical trials with taselisib. All patients should be routinely asked about the occurrence of adverse events which could include new or changed pulmonary symptoms (consistent with lung abnormalities). CT scans and pulmonary function tests should be done, as clinically indicated, or if there are symptoms that indicate that the patient has developed pneumonitis. In case of a documented pneumonitis, the guidelines (including dose

modifications) in the table above should be followed. Consultation with a pulmonologist is highly recommended for any pneumonitis case during the study.

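### The Section 7.2 rule for restarting after both drugs are held is not reconciled with the event-specific rules in Tables 2 and 3 and Sections 7.2.1.5 and 7.3.2

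*Combined protocol and SAP*

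**What the plan says.** Section 7.2 points to Table 3 for taselisib dose changes and then adds general rules of its own. Two of them let taselisib go back up:

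- *Attribution rule.* If taselisib was reduced for an event later put down to enzalutamide, and enzalutamide has been stopped, "taselisib can be re-escalated at the discretion of the treating physician after consultation with the Protocol Chair".
- *Joint-hold rule*, later in the same paragraph. If both drugs are held for an adverse event, enzalutamide restarts at its original dose and taselisib one level below its last dose. Then: "After 28 days, if the patient is tolerating both medications well, taselisib may be increased back to the original dose".

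The event-specific rules are elsewhere:

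- Table 3, first grade 3 rash: on resolution to grade 1 or less, "reduce to next lower dose level".
- Table 3, first grade 3 diarrhea or colitis: after recovery and any steroid or antibiotic course, "resume taselisib treatment at one dose level lower".
- Table 3, other clinically significant grade 3 events: hold, then one level lower.
- Table 3, grade 3 hematologic toxicity: current dose if resolved within 7 days, otherwise one level lower.
- Section 7.2.1.5, liver: "A dose reduction should then be administered following resolution of any or all of these liver enzyme abnormalities". A further elevation leads to a second reduction, and abnormalities that remain after two reductions take the patient off study.
- Section 7.3.2, enzalutamide: for toxicities at or above "grade 3, except for anemia, treatment should be withheld until resolution to" grade 1 (or a higher baseline grade), followed by reinstatement one level lower if medically appropriate.

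On dose levels, Section 6.3 says that "the recommended dose of taselisib for phase II is 4 mg". Table 2 gives taselisib 4 mg, then 2 mg, then discontinuation, and enzalutamide 160 mg, 120 mg, 80 mg, then discontinuation. Section 7.4 adds: "Any consideration to modification of the above dose modification guidelines should be discussed with the Protocol Chair for approval or disapproval in advance".

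**The concern.** The joint-hold rule applies to any adverse event for which both drugs are stopped, so it overlaps with almost every row that leads to a hold. The overlap is realistic on the combination arm. Section 7.3.2 withholds enzalutamide for grade 3 or higher toxicity other than anemia, and Table 3 holds taselisib for most grade 3 events. One event can therefore stop both drugs and bring two sets of instructions into play, with no statement of which comes first.

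The safeguards also differ. The attribution rule requires the Protocol Chair to be consulted. Table 3 involves the Chair even when restart at a lower level is considered after a recurrent grade 3 rash, or after symptomatic grade 3 or any grade 4 hyperglycemia. Return to the original dose under the joint-hold rule, with both drugs continuing, asks for no such step.

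At stake is a patient-safety instruction. After the same event, two investigators who both follow the protocol could give different doses, and could differ on whether a recurrence ends taselisib.

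**Working it through.** The plan states no figure on this point, so the check sets the passages side by side. The inputs are the Table 2 levels and the rules listed above. Each row assumes a phase II patient at 4 mg taselisib and 160 mg enzalutamide, a first event, and both drugs held.

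| Event | Event-specific rule | Joint-hold rule (7.2) | Result |
|---|---|---|---|
| Toxicity of grade 3 or more, enzalutamide restart | 7.3.2: 120 mg | 160 mg | Direct conflict |
| Grade 3 hematologic, resolved in 7 days or less, taselisib restart | Table 3: 4 mg | 2 mg | Direct conflict |
| Grade 3 rash, diarrhea/colitis or other, taselisib restart | Table 3: 2 mg | 2 mg | Agree |
| Same events, more than 28 days after restart | Table 3: no return mentioned (2 mg) | 4 mg permitted if both drugs are tolerated | Unreconciled |
| Liver abnormality under 7.2.1.5, later dose | No return mentioned (2 mg) | 4 mg permitted if both drugs are tolerated | Unreconciled |

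**Size of the dose differences.** Taselisib: 4 mg / 2 mg = 2, so re-escalation doubles the daily dose. Enzalutamide: 160 − 120 = 40 mg per day, and 40/160 = 25% of the starting dose.

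**Liver recurrence after re-escalation.** Section 7.2.1.5 counts reductions in sequence, and the second taselisib reduction in Table 2 is discontinuation.

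1. If the first reduction was kept, the recurrence occurs at 2 mg. The second reduction is discontinuation, and the text is clear.
2. If the patient had returned to 4 mg, there are two readings. Counting reductions ever made, this is the second one, so taselisib stops. Counting down from the current dose, the next level is 2 mg. No passage chooses between them.

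**Do the cited reductions stand?** No passage says so. Two features suggest it. Where Table 3 means a reduction to be temporary it says so: grade 2 pneumonitis is reduced only until recovery. The liver rule's running count also presumes that the first reduction has not been undone. This is inference, so the taselisib rows after day 28 are marked unreconciled and not contradictory.

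**Does Section 7.4 settle it?** No. It asks for Chair approval of changes to the dose modification guidelines. The joint-hold rule is itself one of those guidelines, so following it is not a departure from them.

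**The case against.** The best answer is that the joint-hold rule is a later, optional step that supplements Table 3. In the rash, diarrhea/colitis, other-event and liver rules both passages restart taselisib one level lower, and nothing forbids going back up. The rule is permissive and has its own safeguard: both drugs must be well tolerated, and the 28 days read most naturally from restart at the lower dose, not from the hold. It can also be said that the two re-escalation rules cover different situations, so their safeguards need not match. All of this is fair. It rules out reading the text as an automatic return to full dose, or as a direct contradiction with the reduced-restart rows.

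Three further inferences are tempting and not supported:

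- *That recurrences after re-escalation have no place in Table 3.* Several recurrence rules count events, not current dose. A second grade 3 diarrhea means discontinuation at any dose. For rash, two rows could both claim the recurrence, which is an overlap and not a gap. The clear gap is in the liver count.
- *That the rule returns patients to full dose after the worst events.* Table 3 requires discontinuation for grade 4 diarrhea, rash, hematologic toxicity, pneumonitis and other events, and for rash with fever. That includes the phase II rash picture in Section 7.2.1.3 (grade 3 or 4 with fever in 7 of 8 combination-arm patients). Grade 4 hyperglycemia is the exception, with resumption at a lower level after discussion with the Chair.
- *That site differences distort the phase II result.* The documents give no basis for this. Section 15.3 plans no direct comparison of arms, and Section 15.7 keeps patients with incorrect drug administration in the clinical benefit analysis.

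The objection does not reach the two direct conflicts on restart dose or the undefined count after re-escalation. Giving the joint-hold rule precedence as the more specific one would settle the restart doses, but no passage says that it has precedence.

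**Conclusion.** The point holds as an unreconciled dosing rule that should be corrected. Two conflicts are outright: the enzalutamide restart dose after grade 3 or higher toxicity (160 mg or 120 mg), and the taselisib restart dose after short grade 3 hematologic toxicity (2 mg or 4 mg). For grade 3 rash, diarrhea/colitis, other grade 3 events and liver abnormalities the restart dose agrees. The dose beyond 28 days can be 2 mg or 4 mg depending on the passage followed, and a liver recurrence after re-escalation has no defined consequence.

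This assumes that one event leads to both drugs being held and that the 28 days run from restart, whose starting point the text does not state. How often joint holds occur is not given, so neither the number of patients affected nor any effect on the trial's results can be estimated. A reader might infer that the reductions were meant to be permanent and that Section 7.2 breaches them. The documents do not say that. No view is taken on which dose or rule is right.

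**What to change.** The sponsor should reconcile the joint-hold rule in Section 7.2 with Table 2, Table 3, Section 7.2.1.5, Section 7.3.2 and the attribution rule in Section 7.2, and state in one place:

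- which rule governs each drug's restart dose when both are held;
- whether a reduction may be reversed, for which events and grades, from what date the 28 days run, and with what approval;
- how a recurrence after re-escalation counts toward the limits in Table 2 and Section 7.2.1.5, and which rash row of Table 3 applies.

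The clinical content of these answers is for the sponsor. The cost is protocol wording, handled as an amendment under Section 14.1. It needs no change to sample size, endpoints or analysis.

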### 7.2.1 Anticipated Toxicities and Management

#### 7.2.1.1 *Hyperglycemia and Metabolic Effect*

Hyperglycemia has been observed in patients who received single-agent taselisib in the single-agent Phase I study. Hyperglycemia has been reversible upon holding taselisib and/or initiation of anti-hyperglycemic medication (e.g., metformin). HbA1c and fasting glucose levels will be monitored at baseline, and as per the study calendar. Patients should be advised to report symptoms associated with hyperglycemia, such as thirst, frequent urination, and blurred vision. Guidelines for dosage modification and treatment interruption or discontinuation for patients who experience hyperglycemia are outlined in Table 3.

#### 7.2.1.3 *Dermatological Toxicity*

Treatment-related rash, including cases of Grade 3 rash, has occurred in patients who received taselisib. This rash is commonly manifested as maculo-papular with or without pruritus. Incidence rate and severity of rash appear to be dose dependent. The rash has resolved upon holding of taselisib and/or supportive therapy (e.g., topical or systemic steroids). Rash and other dermatological events should be closely monitored, and patients with severe rash should be monitored for associated signs and symptoms such as fever and hypotension that may be suggestive of a systemic hypersensitivity reaction. For severe rash, dosing of taselisib should be interrupted, and patients should be treated with supportive therapy per standard of care. Use of topical antihistamine, as well as topical or systemic corticosteroids, may be considered. Dose delay and modification guidelines for patients who experience rash are outlined in Table 3. Of note, no grade 3 or 4 rashes were noted in the phase Ib portion of this study with dose escalation to 8 mg taselisib. However, in the phase II portion with taselisib at 4 mg, 7 of 8 patients on the combination arm experienced a grade 3 or 4 rash with fever within the first 14 days of treatment. No patients who crossed over from enzalutamide to taselisib + enzalutamide experienced the rash, thus the study is amended so that all patients have a 28 day lead-in with enzalutamide prior to starting taselisib (similar to the cross-over arm). The rash resolved in all patients with IV steroids, antihistamines and supportive care.

